6.4.2 Subsequent doses

During the study, the dose will be escalated after review of the safety and tolerability data from previous dose level(s) by the Safety Review Group (SRG) as described in section 8.5.1.

Based on data from mice, the expected therapeutic range in humans is in the order of 0.35 mg to 3.5 mg. The doses planned in Part A have been selected to span the therapeutic range.

The doses to be tested in Part B will be selected by the SRG as describe in section 8.5.1.

The top dose will not exceed 2.8 mg

6.5 Assessment and management of risk

Any safety risk to study participants is mitigated by the following considerations.

- Data from pre-clinical studies suggest that Neumifil is devoid of any significant CNS or cardiovascular effects. Although standalone respiratory safety studies have not been performed, the pharmacology of Neumifil does not suggest any respiratory risk, and no significant lung pathology has been noted in efficacy studies in mice and rats, or in dose range finding studies.
- In the pivotal GLP 28-day repeated dose toxicity study in rats, significant weight loss was observed in animals at the two highest dose levels: 780 and 1040 µg/animal/day (6% in male and 7% in female animals). This adverse effect was found to be reversible after 2 weeks recovery.
- Abnormal respiratory sounds (loud breathing and/or respiratory crackles) were observed at all doses levels, and this ceased after dosing was stopped.
- Mild to moderate inflammatory and reactive changes were found in the nasal mucosa and respiratory tissues, in animals receiving the two highest dose levels of Neumifil, although animals fully recovered after 2 weeks. The NOAEL in rats following 4 weeks of dosing was 2.5 mg/kg/day.
- The available pre-clinical toxicity data indicate an acceptable safety profile for Neumifil. The NOAEL in the Cynomolgus monkey corresponds to a HED of 0.46 µg in humans with a body weight of 60 kg. The proposed starting dose in Part A of 0.028 mg provides a 3587 fold and 10,600 fold margin of safety based on bodyweight or when normalised by nasal surface area respectively. The maximum selected dose provides a 112 and 331 fold margin of safety when calculated according to bodyweight, or when normalised by nasal surface area, respectively. In addition, the starting dose selected for Group B1 in Part B (multiple ascending dose part of the study) will be no higher than the highest dose that caused no safety concerns in Part A.
- Dose escalation will take place only after safety and tolerability data from preceding dose level(s) have been reviewed. There will be an appropriate interval between sequential groups, to allow for review of those data. Dose escalation will be halted if the stopping criteria are met (see section 8.4.2).
- As Neumifil has never been given to humans before, each new ascending dose will be staggered: sentinel subject will be dosed first, and the remaining subjects will be dosed at least 23 h later.
- If the dose level selected is no higher than one that has already been shown to cause no safety concerns, sentinel subjects will not be required, and subjects will be dosed at intervals of at least 10 min. The maximum dose will not exceed 2.8 mg.
- As this is a first-in-human study, the investigator must obtain a reply from the GP, or have a valid GP reply on file, before dosing a subject (Part A).

- Only subjects who are identified as healthy in respect of major organ classes, as assessed by their medical history, and clinical and laboratory variables will be included in the study.
- Subjects with presence or history of respiratory disease will be excluded from the study. Respiratory function will also be assessed in the form of spirometry at screening.
- Subjects will be monitored frequently throughout the study for safety and tolerability. The safety monitoring practices employed by this protocol are adequate to protect the subjects' safety and should detect all expected treatment emergent adverse events (TEAEs).
- HMR is accredited by the Medicines and Healthcare products Regulatory Agency (MHRA) to do first-in-human studies and will follow its standard operating procedures (SOPs).
- HMR maintains its own resuscitation team (SOP SS329) to deal with medical emergencies, including anaphylaxis and cardiac arrest. The team will be on duty continuously, until at least 24 h after each dose.
- Any risks are adequately mitigated by safety assessments, and by the medical cover provided by the investigator site, and by appropriate IMP manufacture, according to Good Manufacturing Practice (GMP).
- There will be no direct health benefit for study participants from receipt of study medication. An indirect health benefit to the healthy subjects enrolled in this trial is the free medical examination received at screening and during the study.
- The overall risk benefit balance is considered to be acceptable.

6.5.1 *Conducting the trial during the COVID-19 pandemic*

The principal investigator and sponsor have reviewed the risks of conducting the trial in light of the current COVID-19 pandemic. The first priority is the safety of trial subjects and staff, but we also have an ethical duty to preserve the scientific integrity of the trial as far as possible.

Neumifil is a potential medication against SARS-CoV-2 infection, although this study is in healthy volunteers and no benefit is expected. Preliminary non-clinical data indicate that Neumifil can protect recipient animals (Syrian hamster) against infection by SARS-CoV-2 and therefore no specific risks to participants due to conducting the study during the COVID-19 pandemic are anticipated. Non-clinical work in mice, has shown that pre-treatment of mice with Neumifil, before a lethal influenza challenge, protects mice from the viral challenge and does not reduce the development of protective immune responses against the influenza strain. Therefore, it is not anticipated that Neumifil will attenuate the immune response to a vaccine. No interaction between Neumifil and vaccinations against COVID-19 are anticipated.

The purpose of this study is to assess safety and tolerability of Neumifil; to avoid an overlap of adverse events, the administration of Neumifil will not be within 7 days of

a vaccination against COVID-19. Subjects will be resident in the HMR Phase 1 unit for the dosing period. Avoiding administering Neumifil within 7 days of a COVID-19 vaccination will mean subjects in Part A will have a 14-day window (Day -7 to Day 8 with dosing on Day 1) when they will not be eligible for the study if they have a COVID-19 vaccination booked. In Part B there will be a 21-day window (Day -7 to Day 15 with dosing on Day 1) when they will not be eligible for the study if they have a COVID-19 vaccination booked.

This clinical trial will be done in accordance with HMR's COVID-19 risk mitigation policy (RMP), which documents HMR's COVID-19 virus testing strategy for volunteers and staff, social distancing measures, and management of COVID-19-like symptoms. HMR's RMP was first notified to the MHRA and Health Research Authority (HRA) on 22 May 2020, and applies across all HMR's trials. The mitigation measures specified in the HMR COVID-19 RMP are deemed adequate for this trial. Any deviations from the RMP will be documented in a separate COVID-19 trial-specific risk assessment, prepared by the investigator. Any deviations from the protocol that result from the COVID-19 pandemic, and COVID-19 related AEs or SAEs, will be documented.

Taking the above factors into account, and the proposed mitigation, we believe that it is medically and ethically acceptable to proceed with the trial during the current COVID-19 pandemic.

7 Objectives and endpoints

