The planned dose levels are: 0.028 mg (Group A1), 0.085 mg (Group A2), 0.28 mg (Group A3), 0.885 mg (Group A4), and 2.8 mg (Group A5). Because Neumifil has never been given to humans before, each new ascending dose will be staggered via the use of sentinel subjects. It is intended that subsequent groups will receive higher doses. The dose will be escalated only if the safety and tolerability of the previous highest dose are acceptable, as determined by the Safety Review Group (SRG). Additional dose levels may be explored in up to 2 optional groups of 9 subjects (Groups A6 and A7).

Subjects will be screened within 35 days before their dose of trial medication. Subjects will be resident on ward from 1 day before their dose (Day –1) until about

24 h after dosing (Day 2). They will return for a follow-up visit 7–8 days after their dose (Day 8–9).

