6.2.5 Toxicology

In the rat dose-range finding study, systemic exposure to Neumifil could not be determined because too few plasma samples had concentrations above LRQ. Rats received intranasal doses up to 1000 µg/day for 7 days, and there were no treatment-related deaths or significant clinical observations. However, some female rats had a slight decrease in body weight gain (average 3%), attributed to decreased food consumption. The maximum tolerated dose was 1000 µg/animal/day.

In the pivotal Good Laboratory Practice (GLP) 28-day repeated dose toxicity study in rats, animals received intranasal doses of 520, 780, and 1040 µg/animal/day, but again few samples had plasma Neumifil concentrations above LRQ. The following pharmacokinetic parameters were estimated for Day 28: C_{max} 123 ng/mL; t_{max} 2 h; and AUC 381 ng.h/mL. No animal died, but significant weight loss occurred at the 2 highest dose levels (6% in males and 7% in females). That adverse effect was reversible after 2 weeks' recovery. Abnormal respiratory sounds (loud breathing and/or respiratory crackles) were observed at all dose levels but remitted after dosing was stopped. Mild to moderate inflammatory and reactive changes in the nasal mucosa, associated with polymorphonuclear cell infiltration and goblet cell proliferation, were found in all treatment groups but were considered adverse only at the mid and top dose levels. Inflammatory changes were noted also in respiratory tissues (larynx, trachea, bronchi and bronchioles) at the 2 highest dose levels of Neumifil, but animals recovered fully after 2 weeks. The no observed adverse effect level (NOAEL) in rats after 4 weeks' dosing was 2.5 mg/kg/day.

In a non-GLP dose-range finding study, Cynomolgus monkeys received doses up to 1.25 mg/kg/day for 7 days. There were no treatment-related deaths or significant clinical findings.

Doses of 0.8, 1.20 and 1.65 mg/kg/day were tested in a GLP 28-day repeated dose Cynomolgus monkey toxicity study. All plasma concentrations of Neumifil were below LRQ. There were no deaths, and no effects related to the test item. ADA analysis showed weak seroconversion in 4 animals, but ADA titres were similar to those in untreated animals, so Neumifil was of low immunogenicity. The NOAEL in Cynomolgus monkeys after 4 weeks' dosing was 1.65 mg/kg/day.

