6.4 Rationale for choice of dose(s)

6.4.1 Starting dose

In the absence of the viral target, the minimum anticipated biological effect level (MABEL) is not relevant in calculating the starting dose. Instead, the safety-focused no observed adverse effect (NOAEL) approach was used.

As is typical for molecules dosed intranasally⁸, the margin of safety was calculated based on both systemic and local toxicity. The Human Equivalent Dose (HED) was not corrected for body surface area, as HEX17 is a recombinant protein of molecular weight 162 kD, and proteins are typically normalised on a mg/kg basis without allometric scaling.

The NOAELs in the 28-day GLP toxicology studies in rats and Cynomolgus monkeys were 2.5 mg/kg/day and 1.65 mg/kg/day, respectively. The monkey is the more sensitive species and is also the more relevant for humans with respect to nasal structure and toxicity⁹, so was used to calculate safety margins. The margins of safety for the planned first dose and maximum intended clinical dose, calculated for systemic toxicity (mg/kg/day) and local toxicity (mg/kg/cm²) are shown, respectively, in Table 1 and Table 2.

Table 1 Calculation of margins of safety for Neumifil, based on mg/kg bodyweight

	Monkey	Planned first clinical dose (28 µg)	Maximum intended clinical dose (885 µg)
Dose at NOAEL	1650 µg/kg/day	n/a	n/a
HED (µg/kg/day; calculated for a 60 kg person)	n/a	0.46 µg	14.75 µg
MoS on µg/kg/day basis	n/a	3587 fold	112 fold

HED: Human equivalent dose; MoS: Margin of Safety; NOAEL: No Observed Adverse Effect Level

Table 2 Calculation of margins of safety for Neumifil, normalised by nasal surface area

	Monkey	Planned first clinical dose (28 µg)	Maximum intended clinical dose (885 µg)
Dose at NOAEL	1650 µg/kg/day	n/a	n/a
HED (µg/kg/day; calculated for a 60 kg person)	n/a	0.46 µg	14.75 µg
Dose normalised by species-specific nasal surface area ¹ (µg/kg/cm ²)	26.78	0.0025 µg	0.081 µg
MoS on µg/kg/cm ² basis	n/a	10,600 fold	331 fold

HED: Human equivalent dose; MoS: Margin of Safety; NOAEL: No Observed Adverse Effect Level

¹ 61.6 cm² in monkey; 181 cm² in human

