8.1.1 Part A

Enrolment of up to 36 healthy subjects is planned, in up to 5 groups (Groups A1–A5). Groups A1–A3 will consist of 6 subjects each, and Groups A4 and A5 will consist of 9 subjects each.

Subjects will receive a single intranasal dose of Neumifil or placebo. In Groups A1–A3, 4 subjects will receive Neumifil and 2 will receive matching placebo. In Groups A4 and A5, 6 subjects will receive Neumifil and 3 will receive matching placebo. Additional dose levels may be explored in up to 2 optional groups of up to 9 subjects each.

The starting dose for Group A1 is 0.028 mg Neumifil. Subsequent planned doses are given in Table 3.

Table 3 Planned doses in Part A

Group	Planned nominal dose of Neumifil	Number of subjects	Number on placebo
A1	0.028 mg	6	2
A2	0.085 mg	6	2
A3	0.28 mg	6	2
A4	0.885 mg	9	3
A5	2.8 mg	9	3
A6 (optional)	To be decided	9	3
A7 (optional)	To be decided	9	3

Because Neumifil has never been given to humans before, each new ascending dose will be staggered: sentinel subjects will be dosed first, and the remaining subjects will be dosed at least 23 h later. To maintain the blind nature of the study, the 2 sentinel subjects will be randomised to ensure that 1 subject receives active treatment and the other receives placebo. Since 1 subject will receive placebo treatment, the sentinel subjects may be dosed at least 5 min apart. Provided the investigator considers the safety and tolerability in the sentinel subjects to have been acceptable, the remaining subjects will be dosed, at intervals of at least 10 min.

The planned dose levels may be changed, depending on the safety and tolerability results after previous doses, as described in section 8.5. The dose will not be escalated unless the safety and tolerability of the previous dose is acceptable. There will be an appropriate interval between sequential groups, to allow for review of those data. If the dose level selected is no higher than one that has already been shown to cause no safety concerns, sentinel subjects will not be required, and subjects will be dosed at intervals of at least 10 min. The maximum dose will not exceed 2.8 mg.

Subjects will be screened within 35 days before their dose of trial medication.

Subjects will be resident on ward from 1 day before their dose (Day –1) until about 24 h after dosing (Day 2). They will return for a follow-up visit 7–8 days after their dose (Day 8–9).

8.1.2 *Part B*

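### The safety margins given for the maximum dose (112-fold and 331-fold) belong to 885 µg; at the planned and capped maximum of 2.8 mg they are about 35-fold and 104-fold

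*Combined protocol and SAP*

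**What the plan says.** Section 6.2.5 gives the basis for the margins: "The NOAEL in Cynomolgus monkeys after 4 weeks' dosing was 1.65 mg/kg/day". Section 6.4.1 explains that the monkey is the more sensitive and more relevant species, "so was used to calculate safety margins", and that doses are compared per kilogram without allometric scaling. Tables 1 and 2 then have one column for the 28 µg starting dose and one headed "Maximum intended clinical dose (885 µg"). For the latter they give 112-fold by body weight and 331-fold by nasal surface area.

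Section 6.5 carries these figures into the assessment of risk to participants: "The maximum selected dose provides a 112 and 331 fold margin of safety when calculated according to bodyweight", with 331 being the surface-area figure. Just before that, it says that the monkey NOAEL "corresponds to a HED of 0.46 µg in humans with a body weight of 60 kg".

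The dosing sections use a different maximum. The list of Part A doses in section 2.5.1 puts 0.885 mg in Group A4 and ends "and 2.8 mg (Group A5"); Table 3 agrees. Section 6.4.2 says "The top dose will not exceed 2.8 mg", and section 8.1.1 says "The maximum dose will not exceed 2.8 mg". Section 6.5 itself and section 8.5.2 repeat the same limit. Section 8.5.3 lets Part B go up to the highest single Part A dose that raised no safety concern, for a planned 7 days and at most 14.

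**The concern.** The risk assessment attaches to the maximum dose a margin calculated for the second-highest planned dose. Section 6.5 contradicts itself: it quotes the 885 µg margins and, a few bullets later, sets the limit at 2.8 mg. A reader who relies on section 6.5, such as an ethics committee member or the regulator, would take the top dose to have more than 100-fold cover by body weight. It does not, on the protocol's own method.

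These are the only numerical safety margins given for the upper end of the dose range. The participants are healthy volunteers with no direct benefit. Exposure at 2.8 mg may also be repeated, because Part B can reach that dose. The local margin matters for a nasal product: section 6.2.5 reports nasal mucosal changes in all treated rat groups, judged adverse at the middle and top doses.

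The sentence on the human equivalent dose adds confusion. Read literally, it makes the 28 µg starting dose about 61 times the human equivalent of the NOAEL (28/0.46 = 60.9), which cannot be squared with the 3587-fold margin stated next.

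**Working it through.** **Inputs**
- Monkey NOAEL: 1650 µg/kg/day (section 6.2.5; Tables 1 and 2)
- Body weight: 60 kg (Tables 1 and 2)
- Nasal surface area: 61.6 cm² in monkey, 181 cm² in human (footnote to Table 2)
- Doses: 28 µg (A1), 885 µg (A4), 2800 µg (A5 and the cap)

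**Formulas, as the tables use them**
- Body-weight margin = 1650 / (dose/60)
- Surface-area margin = (1650/61.6) / ((dose/60)/181)

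**Step 1: reproduce the stated figures at 885 µg**
- 885/60 = 14.75 µg/kg; 1650/14.75 = 111.9 (stated 112).
- 14.75/181 = 0.0815 µg/kg/cm²; 26.79/0.0815 = 328.7. With the table's rounded entries, 26.78/0.081 = 330.6 (stated 331).

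The arithmetic in the tables is right for 885 µg.

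**Step 2: the same formulas at 2.8 mg**
- 2800/60 = 46.67 µg/kg; 1650/46.67 = 35.4.
- 46.67/181 = 0.2578 µg/kg/cm²; 26.79/0.2578 = 103.9.

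| Basis | Stated for the maximum | At 885 µg | At 2.8 mg | Stated / value at 2.8 mg |
|---|---|---|---|---|
| Body weight | 112 | 111.9 | 35.4 | 3.17 |
| Nasal surface area | 331 | 328.7 | 103.9 | 3.19 |

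The dose ratio is 2800/885 = 3.16. The last column differs slightly from it because the stated figures are rounded.

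**Step 3: a check from the protocol's own margins.** The cap is exactly 100 times the starting dose (2800/28). Dividing the stated starting-dose margins by 100 gives 3587/100 = 36 and 10,600/100 = 106. These agree with step 2 and not with 112 and 331.

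**Step 4: the human equivalent of the NOAEL.** On the per-kilogram basis that the protocol adopts, 1650 × 60 = 99,000 µg = 99 mg. The quoted 0.46 is 28/60 = 0.467 µg/kg, cut to two decimals: it is the starting dose per kilogram. Tables 1 and 2 put the clinical dose per kilogram in a row labelled HED, and section 6.5 repeats that label and drops the per-kilogram unit.

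**Step 5: starting-dose margins.** Without intermediate rounding they are 1650/0.4667 = 3536 (stated 3587) and 26.79/0.002578 = 10,389 (stated 10,600), so the stated values are 1.5% and 2.0% high. The cut to 0.46 explains 3587 (1650/0.46 = 3587). The figure of 10,600 does not follow exactly from the table's rounded entry either (26.78/0.0025 = 10,712). This is a minor rounding matter.

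**The case against.** The strongest objection is that little depends on the wrong figures. No dose, escalation step or stopping rule is derived from 112 or 331. Section 6.4.2 justifies the upper doses by an expected therapeutic range of 0.35 to 3.5 mg, and the tables stand under the starting-dose heading. Reaching 2.8 mg is controlled separately by sentinel dosing, review of at least four evaluable subjects on active treatment, a 3.5-fold limit on each step, and stopping criteria. The comparator is a 28-day NOAEL that was the highest dose tested in monkeys and showed no drug-related effect, whereas people receive one dose or at most 14 days of dosing. Margins of 35 and 104 are still large. All of this stands and limits the practical consequence. None of it makes the stated figures correct for the top dose.

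A second objection is that the column heading could refer to a later therapeutic dose and not to this trial's maximum. Section 6.5 does not allow that reading: it applies the margins to the maximum selected dose in an assessment of risk to these participants, next to the Part A starting dose. Nor is 885 µg the top of the expected therapeutic range.

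It is also fair to say that the HED sentence is a separate slip. It does not enter the calculation of 112 or 331, and it errs toward making the drug look less safe.

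**Conclusion.** The concern holds. The margins stated for the maximum dose are those of Group A4. For the highest dose that the protocol plans and permits, the same method gives about 35-fold by body weight and 104-fold by nasal surface area, so the stated values are about 3.2 times too favourable. The documents give no margin at 2.8 mg. The HED sentence is also wrong: 0.46 is the starting dose in µg/kg, and the NOAEL scales to 99 mg for a 60 kg person.

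This rests on the protocol's own assumptions: the monkey NOAEL, 60 kg body weight, no allometric scaling, and the two surface areas in Table 2. It does not show that 2.8 mg is unsafe. It shows that a specific safety statement in a first-in-human risk assessment is contradicted by the dosing plan in the same document, and it needs correction.

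**What to change.** The sponsor should first state which maximum is intended.

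- **If 2.8 mg stands:** replace the 885 µg column in Tables 1 and 2 with 2800 µg (46.67 µg/kg, 35-fold; 0.258 µg/kg/cm², 104-fold), or add a column for it. Give 35-fold and 104-fold in section 6.5, and reconsider the risk statement on those figures.
- **If 885 µg was meant:** lower the limit in sections 6.4.2, 6.5, 8.1.1 and 8.5.2, and remove the 2.8 mg dose from Group A5 in section 2.5.1 and Table 3.

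In either case, correct the HED sentence to 99 mg for a 60 kg person, relabel the HED row in both tables as the clinical dose per kilogram, and give the starting-dose margins from unrounded values (3536 and 10,389).

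Under the first option the cost is two table columns and a few sentences, with no change to the design; the published margins become less favourable. The second option changes the planned dose range.

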7.1 Objectives

7.1.1 Primary objectives

Part A

- To assess the safety and tolerability of single-ascending intranasal doses of Neumifil in healthy subjects.

Part B

- To assess the safety and tolerability of multiple-ascending intranasal doses of Neumifil in healthy subjects.

7.1.2 Exploratory objective

- To determine the number of subjects contracting SARS-CoV-2 during the 7 days after receiving their (last) dose.
- To assess the formation of Neumifil ADAs after multiple-ascending intranasal doses in healthy subjects (Part B only).

- To assess the plasma concentration of single- or multiple-ascending intranasal doses of Neumifil in healthy subjects to determine if intranasal administration results in systemic exposure.
- To assess the concentrations of cytokines and chemokines in nasal secretions before dosing and after multiple intranasal doses of Neumifil (Part B only).

